8.5.2 Analysis methods for non-immunogenicity endpoints

Change from baseline in ACQ-6 score will be summarized by timepoint. ACQ-6 asthma control responder status will be summarized at Week 12 (EOT) by treatment group according to the following limits:

- ACQ-6 (EOT) \leq 0.75 \rightarrow Well controlled
- 0.75< ACQ-6 (EOT) \leq 1.5 \rightarrow Partly controlled
- ACQ-6 (EOT) \geq 1.5 \rightarrow Not well controlled

All analyses will be based on the full analysis set.

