1.4 Study design

This is a randomized, double-blind, parallel group, placebo-controlled study designed to investigate the potential effect of a fixed dose of benralizumab (30 mg) administered SC on the humoral immune response following seasonal influenza virus vaccination.

Approximately 100 patients 12-21 years of age with severe asthma will be randomized to receive SC benralizumab 30 mg or placebo administered at Weeks 0, 4, and 8. Fifty percent or more of the patients will be 12 to 17 years of age.

Patients will receive 1 dose of seasonal influenza virus vaccine IM at Week 8. Samples for evaluation of antibody response will be drawn at Week 8 and Week 12.

After enrolment and confirmation of entry criteria, patients will proceed to screening period of a minimum of 2 weeks to allow adequate time for all of the eligibility criteria to be evaluated. Patients who continue to meet the eligibility criteria will be randomized at Week 0 to receive 3

SC doses (at Weeks 0, 4, and 8) of benralizumab 30 mg or placebo. Patients will receive 1 dose of seasonal influenza virus vaccine IM at Week 8. Samples for evaluation of antibody response will be drawn at Week 8 and Week 12. The End of Treatment (EOT) will be conducted at Week 12 and a Follow-up (FU) visit will be conducted at Week 20.

Patients will be maintained on their currently prescribed ICS-LABA therapy(ies) without change from enrollment throughout the screening and treatment period.

Figure 1 Study flow chart

	_				
Visit 7 Follow-up		FU Visit Week 20		FU Visit Week 20	
ponse nd of ıt	Г				1
Visit 6 Antibody Response Evaluation/End of Treatment		ARE/EOT Visit Week 12		ARE/EOT Visit Week 12	l
Anti	_	企		む	_
Double-blind Randomized Treatment Period Visits 3 – 5	Vaccination Visit 5 (Week 8)	50 Subjects SC Benralizumab 30 mg at Weeks 0, 4, 8, (3 doses)		50 Subjects SC Placebo at Weeks 0, 4, 8 (3 doses)	
Visit 3 (Week 0)	<		Randomization 100 Subjects in 1:1 ratio		>
Visit 2			Screening 2 - 3 wooks	Nagara Magaza	
Visit 1			Scre		

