2.2 Secondary Objectives

Objective	Endpoint		
To further evaluate the potential effect of benralizumab on the humoral immune response following seasonal influenza virus	• Proportion of patients who achieve a strain- specific post-dose HAI antibody titer ≥320 at Week 12		
vaccination in adolescent and young adult patients with severe asthma	Post-dose strain-specific microneutralization (MN) antibody GMFRs from Week 8		
	Post-dose strain-specific serum MN antibody GMTs obtained at Week 12		
	• Proportion of patients who experience a strain- specific post-dose antibody response at Week 12 with antibody response defined as a ≥4-fold rise in MN antibody titer from Week 8		
To assess the potential effect of benralizumab on asthma control	Change from baseline in mean Asthma Control Questionnaire-6 (ACQ-6) score at Week 12		

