Note: All patients must have reversibility testing performed before randomization to establish a baseline characteristic even if historical documentation is used to meet this criterion.

If historical reversibility is being used to meet this criterion, the relevant historical preand post-bronchodilator results must be entered into the electronic case report form (eCRF).

If patients do not demonstrate airway reversibility at either Visit 1 or Visit 2 and historical reversibility is not available for evidence of asthma, the patient must not enter the treatment period and must be rescreened, if appropriate. If re-screened, the site should reiterate the need to withhold short- and long-acting bronchodilators as required in Section 5.1.2 prior to spirometry visits in an effort to meet this inclusion criterion.

Randomization criteria

- 9. For WOCBP: have a negative urine pregnancy test prior to administration of the IP at Visit 3
- 10. Not well controlled asthma as documented by either
 - An ACQ-6 \geq 1.5 OR
 - A peak flow of 60-80% predicted OR
 - An exacerbation, 1 or more, that required oral corticosteroids in the previous year
 OR
 - Any 1 of the following assessed by patient recall over the previous 2-4 weeks

- Asthma symptoms >2 days/week; OR
- Nighttime awakenings 1 or more/week; OR
- Short acting β_2 -agonist use for symptom control (not for prevention of exercise-induced asthma) >2 days/week.

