3.3 Patient enrolment and randomization

Investigator(s) should keep a record of patients considered for and included in the study. This pre-screening/screening log will be evaluated periodically by AstraZeneca or its delegates during routine monitoring visits.

Each patient should meet all of the inclusion criteria and none of the exclusion criteria for this study. Under no circumstances can there be exceptions to this rule.

The Investigator will:

- 1. Obtain signed informed consent/assent as appropriate with local guidance from the potential patient before any study specific procedures are performed
- 2. Assign each potential patient a unique enrollment number beginning with E# via interactive web/voice response system (IWRS/IVRS)

- 3. Determine patient eligibility
- 4. Assign eligible patient unique randomization code via IWRS/IVRS

If a patient withdraws from participation in the study, then his/her enrolment/randomization code cannot be reused.

Patients will be allocated to treatment arms in a 1:1 ratio. Specific information concerning the use of the IWRS/IVRS will be provided in the separate manual. Randomized patients who discontinue from IP administration will not be replaced.

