5.3.3 Asthma Control Questionnaire (ACQ-6)

The ACQ-6 is a shortened version of the ACQ that assesses asthma symptoms (nighttime waking, symptoms on waking, activity limitation, shortness of breath, wheezing, and short-acting $\beta 2$ agonist use) omitting the FEV₁ measurement from the original ACQ score.

For patients on the ophylline see Section 3.5.2.2.

Patients are asked to recall how their asthma has been during the previous week by responding to 1 bronchodilator use question and 5 symptom questions.

Questions are weighted equally and scored from 0 (totally controlled) to 6 (severely uncontrolled). The mean ACQ-6 score is the mean of the responses. Mean scores of \leq 0.75 indicate well-controlled asthma, scores between 0.75 and \leq 1.5 indicate partly controlled asthma, and a score >1.5 indicates not well controlled asthma (Juniper et al 2006).

The questionnaire will be completed at the study center in accordance with schedule provided in Table 2.

The Investigator's clinical acumen and ACQ-6 results should be used in concert to determine whether or not the patient is well enough to continue in the current clinical study.

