8.4.3 Calculation or derivation of patient reported outcome variables

8.4.3.1 Asthma Control Questionnaire (ACQ-6)

The outcome variable for ACQ-6 will be the change in mean score from baseline (Week 0) to EOT (Week 12).

Asthma control responder status will be categorized according to the following limits (Juniper et al 2005):

- ACQ-6 (EOT) \leq 0.75 \rightarrow Well controlled
- $0.75 < ACQ-6 (EOT) < 1.5 \rightarrow Partly controlled$
- ACQ-6 (EOT) \geq 1.5 \rightarrow Not well controlled

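### Section 8.5.2 fixes only a descriptive summary of ACQ-6 change by timepoint, so the asthma-control objective gets no estimated difference from placebo and no confidence interval

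*Protocol*

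**What the plan says.** Protocol section 2.2 gives the objective as "To assess the potential effect of benralizumab on asthma control". Section 8.4.3.1 defines the variable: "The outcome variable for ACQ-6 will be the change in mean score from baseline (Week 0) to EOT (Week 12)".

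The analysis is in section 8.5.2: "Change from baseline in ACQ-6 score will be summarized by timepoint". The next sentence does name the arms, but only for the categorized score: "ACQ-6 asthma control responder status will be summarized at Week 12 (EOT) by treatment group". The statistical methods in the synopsis do not mention ACQ-6.

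Section 8.5.1, for GMFR and GMT, specifies an ANCOVA on the log scale, a ratio between treatment groups and a 90% CI.

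Randomization criterion 10 in section 3.1 asks for "Not well controlled asthma as documented by either" of several alternatives: ACQ-6 of at least 1.5, a peak flow range, an exacerbation in the previous year, or recalled symptoms, awakenings or reliever use. On timing, section 5.3.3 says: "The questionnaire will be completed at the study center in accordance with schedule provided in Table 2". Table 2 starts ACQ-6 at Visit 3 (Week 0), and Table 1 (screening) does not list it.

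**The concern.** The objective asks for an effect of the drug, which in a placebo-controlled trial means a difference between arms. The ACQ-6 sentence in 8.5.2 asks for a description of change over time. An analysis that followed it to the letter would give mean changes and leave the reader to judge the effect from them.

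Those changes are hard to read alone. Because ACQ-6 is first scheduled at Week 0, a patient who qualifies by a score of 1.5 or more has that same score as baseline. Patients picked for a high value tend to score lower when measured again, treated or not. The ordinary course of asthma adds to this. A fall within the benralizumab arm therefore mixes drug effect with change that would have happened anyway.

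At stake is whether the report of a named secondary objective contains an effect estimate with a stated precision or only columns of within-group change.

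**Working it through.** **1. The plan's own precision figure.** The only one is for the GMT ratio (section 8.2): 50 per arm, SD 1.2 on the natural log scale, observed ratio 1.

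exp(±1.645 × 1.2 × √(2/50)) = exp(±0.395) = 0.674 to 1.484, against 0.67 to 1.48 stated. It reproduces. The protocol gives no precision figure for ACQ-6.

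**2. Size of regression to the mean within an arm.** The inputs are assumptions, since the protocol gives no ACQ-6 mean, SD or correlation. For a normal score with mean μ and SD σ, selected at 1.5 or above, and correlation r with the later score, the expected fall without any treatment effect is

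(1 − r) × σ × φ(a)/(1 − Φ(a)), with a = (1.5 − μ)/σ.

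- σ = 0.9, μ = 1.2: selected mean 2.12, which is 0.92 above μ. Fall 0.09 (r = 0.9) to 0.28 (r = 0.7).
- σ = 0.9, μ = 1.8: selected mean 2.34, which is 0.54 above μ. Fall 0.05 (r = 0.9) to 0.16 (r = 0.7).
- Wider inputs (μ 1.3 to 1.8, σ 0.8 to 1.1, r 0.5 to 0.85): 0.07 to 0.50.

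These figures apply to patients selected on ACQ-6. If half of an arm is so selected and the rest is unselected on ACQ-6, the arm-level fall is about half as large.

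**3. Does it bias the comparison of arms?** Simulation of 5,000 trials with 50 per arm, μ = 1.5, σ = 1.0, r = 0.6, every patient selected at 1.5 or above:

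| True effect | Mean change, benralizumab | Mean change, placebo | Difference | Coverage of 90% CI |
|---|---|---|---|---|
| 0 | −0.320 | −0.319 | 0.000 | 90% |
| −0.40 | −0.719 | −0.319 | −0.400 | 90% |

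The formula in step 2 agrees: here a = 0, so the fall is 0.4 × 0.798 = 0.319. With no drug effect the benralizumab arm still appears to improve by about 0.32. Subtracting placebo removes this, without baseline adjustment.

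**4. Precision of the difference.** Assumptions: SD 1.0 at Week 0 and at Week 12, correlation r, 50 analyzed per arm, t quantile 1.66 (98 df).

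- Raw Week 12 score: 1.66 × 1.0 × √(2/50) = 0.332.
- Unadjusted change score, SD √(2(1 − r)): at r = 0.6, 0.332 × √0.8 = 0.297.
- ANCOVA, residual SD √(1 − r²): at r = 0.6, 0.332 × √(1 − 0.36) = 0.266.

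The endpoint is change, so the fair comparison is 0.297 with 0.266. The ratio of ANCOVA to change score is √((1 + r)/2):

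- r = 0.6: 0.894, a gain of about 11%.
- r = 0.7: 0.922, a gain of about 8%.
- r = 0.9: 0.975, a gain of about 3%.

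**The case against.** The strongest reply is that the trial already contains the answer. Allocation is randomized and concurrent ("Patients will be allocated to treatment arms in a 1:1 ratio"), and both arms pass the same criterion 10. The full analysis set classifies patients by randomized treatment, nothing in 8.5.2 pools the arms, and the responder summary beside it is by treatment group. Mean changes by arm, with n and SD, would let anyone form the difference. No hypotheses are tested, and the model for a descriptive secondary endpoint is commonly left to the SAP, which is not at hand.

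Much of this stands, and it rules out four stronger readings:

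- A reader might infer that regression to the mean cannot be told apart from a benralizumab effect in this trial. That would be so for a before-after reading of one arm. It is not so for the randomized comparison (step 3).
- A reader might infer that only a baseline-adjusted comparison deals with it. An unadjusted one does so in expectation; adjustment adds precision and handles chance imbalance. Nor does a linear baseline term give patients with low starting scores more room to improve.
- A reader might infer that the arms are to be pooled. The text does not say so, and the missing words are probably shorthand.
- A reader might set 0.33 against 0.27 and claim a 20% gain in precision. The 0.33 belongs to the raw Week 12 score, which is not the endpoint.

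The objection does not explain the missing contrast. Under parallel headings on analysis methods, 8.5.1 fixes an estimate with an interval and 8.5.2 fixes a summary. The absence of hypothesis tests does not account for the difference, because 8.5.1 gives intervals without testing. The responder table is no substitute: it is unadjusted, and in 8.5.2 a score of exactly 1.5 falls into two categories.

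**Conclusion.** The point holds as a gap in the stated analysis. It does not show a bias in the design. The protocol sets an objective about a drug effect on asthma control and fixes an ACQ-6 summary that contains no estimate of that effect.

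Within-arm change could include roughly 0.05 to 0.50 points of regression to the mean among patients entering by ACQ-6, and less across a whole arm because the other routes are open. The between-arm difference carries none of this in expectation, and that conclusion does not depend on the assumed values.

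The main gain from the fix is that the objective receives an estimate with an interval. The gain in precision is modest: about a tenth at correlation 0.6 (half-width 0.30 to 0.27), and 8% down to 3% at correlations of 0.7 to 0.9. These figures rest on SD 1.0 at both visits and complete data on 50 patients per arm, none of which the protocol states for ACQ-6. This is a worthwhile improvement at almost no cost.

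**What to change.** In section 8.5.2, replace the sentence on ACQ-6 change with wording to this effect: change from baseline in ACQ-6 will be summarized by treatment group and timepoint; change at Week 12 will be compared between groups by ANCOVA with treatment, Week 0 ACQ-6 and age stratum (12 to 17, 18 to 21 years), giving the least-squares mean difference, benralizumab minus placebo, with a 90% CI; within-group changes are descriptive only.

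This brings ACQ-6 into line with the approach of 8.5.1 and uses the randomization strata of section 6.5. It costs one sentence and one model. The data are already scheduled, and no visit, test or patient is added.

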8.5.3 Analysis methods for safety variables

8.5.3.1 Asthma exacerbations

The number of asthma exacerbations and total follow-up time will be presented for each treatment group. This analysis will be based on the safety analysis set.

8.5.3.2 Other safety variables

AEs will be summarized by means of counts by study period (on-study, on-treatment, and follow-up period). AEs will be listed for each patient and summarised by System Organ Class (SOC) and Preferred Term (PT) assigned to the event by MedDRA.

Laboratory data for hematology and clinical chemistry will be summarized. The frequency of changes with respect to normal ranges between baseline and each post-treatment time point will be tabulated. Frequencies of clinically noteworthy values (defined in the SAP) occurring during the clinical study will also be given. Shifts from normal to abnormal between baseline and each post-baseline time point will be evaluated for urinalysis. Changes in vital signs will be examined at each visit by endpoint and frequencies of clinically noteworthy values will also be presented. Shifts from normal to abnormal between baseline and follow-up will be evaluated for the physical examination.

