	• Proportion of patients who experience a strain-specific post-dose antibody response at Week 12 with antibody response defined as a ≥4-fold rise in HAI antibody titer from Week 8
	• Proportion of patients who achieve a strain-specific post-dose HAI antibody titer ≥40 at Week 12

(b) Secondary Objectives

Objective	Endpoint(s)
To further evaluate the potential effect of benralizumab on the humoral immune response following seasonal influenza virus vaccination in adolescent and young adult patients with severe asthma	• Proportion of patients who achieve a strain-specific post-dose HAI antibody titer ≥320 at Week 12
	Post-dose strain-specific microneutralization (MN) antibody GMFRs from Week 8
	Post-dose strain-specific serum MN GMTs obtained at Week 12
	• Proportion of patients who experience a strain-specific post-dose antibody response at Week 12 with antibody response defined as a ≥4-fold rise in MN antibody titer from Week 8
To assess the potential effect of benralizumab on asthma control	Change from baseline in mean Asthma Control Questionnaire-6 (ACQ-6) score at Week 12

(c) Safety Objective

Objective	Endpoint
To assess the safety and tolerability of benralizumab	Adverse events (AEs) and serious adverse events (SAEs)
	Laboratory variables
	Physical Examination

Study design

This is a randomized, double-blind, parallel group, placebo-controlled study designed to investigate the potential effect of a fixed dose of benralizumab (30 mg) administered subcutaneously (SC) on antibody responses following seasonal influenza virus vaccination.

Approximately 100 patients 12-21 years of age with severe asthma will be randomized to receive SC benralizumab 30 mg or placebo administered at Weeks 0, 4, and 8.

After enrolment and confirmation of entry criteria, patients will proceed to a screening period of a minimum of 2 weeks to allow adequate time for all of the eligibility criteria to be evaluated before being randomized at Visit 3. Patients who continue to meet eligibility criteria will be randomized on Week 0 to receive 3 SC doses (at Weeks 0, 4, and 8) of benralizumab 30 mg or placebo. Patients will receive 1 dose of seasonal influenza vaccine intramuscularly (IM) at Week 8. Serum samples for evaluation of antibody response will be drawn at Week 8 and Week 12. An End of Treatment (EOT) will also be conducted at Week 12 and a Follow-up visit will be conducted at Week 20.

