4. STUDY PLAN AND PROCEDURES

Table 1 Study Plan – Enrollment, screening period

		Screening			
	D.C.	V1	V2ª		
Assessment/ activity	Refer to	(W -4 to W -2)			
Informed consent/assent	10.4	X			
Inclusion/exclusion criteria	3.1/3.2	X	X		
Medical and asthma history b	4.1.1	X			
Complete physical examination	5.2.1.1	X			
Weight, Height, BMI	5.3.1	X			
Vital Signs	5.2.2	X	X		
Local ECG	5.2.3	X			
Serum chemistry	5.2.4	X			
Hematology	5.2.4	X			
Urinalysis	5.2.4	X			
Serum concentration (theophylline) ^c	3.5.2.2	X			
Serology (hepatitis B,C; HIV-1; HIV-2)	5.3.4.1	X			
Serum pregnancy test	5.2.4.1	X			
Pre-bronchodilator FEV ₁ d	5.1.2.1	X	X		
Post-bronchodilator FEV ₁ ^d	5.1.2.1	X	X		
Adverse events	7.1	X	X		
Concomitant medication	3.5	X	X		

Visit 1 and Visit 2 can be combined if the patient has the time and they have not taken SABAs for 6 hours or their long-acting bronchodilator-containing therapy for 12-24 hours. If spirometry/reversibility procedures are actually planned at Visit 1 as a convenience, then the ICF/assent must be signed prior to Visit 1 and prior to instructing the patient to withhold any medication.

To include influenza vaccination history.

For patients on the ophylline (see Section 3.5.2.2)

Pre- and post-bronchodilator spirometry can be done at Visit 1 OR Visit 2. If patients do not demonstrate airway reversibility at either Visit 1 or Visit 2 and this is needed to qualify the patient for randomisation, the site should screen fail the patient.

BMI Body mass index; D Days; ECG Electrocardiogram; HIV Human immunodeficiency virus; V Visit; W Week.

Table 2 Study Plan – Randomization, treatment period, and follow-up

	Refer to	Treatment			ARE/EOT	IPD	FU	Unsch
		V3	V4	V5	V6		V7	
Assessment/ activity		W0	W4	W8	W12		W20	
			Visit window (days) ^a					
		±0	±3	±3	±3	±3	±3	
Inclusion/exclusion criteria	3.1/3.2	X						
Randomization	3.3	X						
Administration of investigational product ^c	6.8	X	X	X				
Administration of influenza vaccine ^e				X				
Complete physical examination	5.2.1.1	X			X	X	X	
Brief physical examination	5.2.1.2		X	X				X
Vital Signs	5.2.2	X	X	X	X	X	X	X
ACQ-6	5.3.3	X	X	X	X	X		
Asthma exacerbation assessment	5.3.2	X	X	X	X	X	X	X
Adverse events	7.1	X	X	X	X	X	X	X
Concomitant medication	3.5	X	X	X	X	X	X	X
Serum chemistry	5.2.4	X			X	X	X	
Hematology	5.2.4	X			X	X	X	
Urinalysis	5.2.4	X			X	X	X	
Urine pregnancy test (dipstick) b	5.2.4.1	X	X	X	X	X	X	
PK	5.3.5	X		X	X	X	X	
ADA	5.3.7	X		X	X	X	X	

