4.3 Follow-up period

Patients who complete the double-blind randomized treatment period will be followed for 12 weeks after the last dose of IP for the Week 20 follow-up visit.

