5.2 Safety assessments

5.2.1 Physical examination

Physical examination will be done in accordance with the schedules provided in Table 1 and Table 2.

Baseline data will be collected at Visit 1. Any new finding(s) or aggravated existing finding(s), judged as clinically significant by the Investigator, will be reported as an AE as described in Section 7.1.

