5.2.1.2 Brief physical examination

The brief physical examination includes an assessment of the general appearance, abdomen, cardiovascular, and respiratory system. For the brief physical examination only information on whether the assessment was performed or not is to be recorded.

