8.4.2 Calculation or derivation of safety variable(s)

The following safety data will be collected: vital signs, physical examination, hematology, clinical chemistry, urinalysis, and reported AEs.

Change from baseline (Week 0) to each post-treatment time point where scheduled assessments were made will be calculated for relevant measurements. Adverse events will be summarized by means of descriptive statistics and qualitative summaries.

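### Physical-examination shifts appear to be tabulated only from baseline to Week 20, leaving the recorded Week 12 and premature-discontinuation examinations out of the shift table

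*Protocol*

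**What the plan says.** Protocol 2.3 lists physical examination as an endpoint of the safety objective, beside adverse events and laboratory variables. Protocol 8.5.3.2 states how it is to be analysed: "Shifts from normal to abnormal between baseline and follow-up will be evaluated for the physical examination".

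The other safety data in that paragraph are treated differently. For urinalysis the rule is "Shifts from normal to abnormal between baseline and each post-baseline time point will be evaluated for urinalysis". Laboratory changes against normal ranges are tabulated at each post-treatment time point, and vital signs are examined at each visit.

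Table 2 schedules complete examinations at Week 0, Week 12 (ARE/EOT), the IPD visit and the follow-up visit at Week 20. Weeks 4 and 8 and unscheduled visits have a brief examination, for which 5.2.1.2 says: "For the brief physical examination only information on whether the assessment was performed or not is to be recorded".

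On who attends Week 20, 4.3 says: "Patients who complete the double-blind randomized treatment period will be followed for 12 weeks after the last dose of IP". Sections 3.6 and 4.2 send patients who stop IP early to the IPD visit and do not mention Week 20.

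On baseline, 5.2.1 says "Baseline data will be collected at Visit 1", while 8.4.2 speaks of "Change from baseline (Week 0) to each post-treatment time point" for relevant measurements.

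**The concern.** The shift table is the only display the protocol specifies for physical examination as an endpoint in its own right. If it compares baseline with Week 20 alone, it describes patients 12 weeks after their last dose and omits the Week 12 examination, made 4 weeks after it. An abnormality present at Week 12 and gone by Week 20 would not appear. Nor would one found at the IPD visit in a patient with no Week 20 examination, although that patient belongs to the safety analysis set (8.3.4).

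These examinations are already scheduled and recorded. What is at stake is whether they are shown by treatment group.

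**Working it through.** The protocol gives no figure to reproduce. The check sets the passages side by side and applies the rule to example records.

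**Step 1: what follow-up means in 8.5.3.2.** The synopsis says "a Follow-up visit will be conducted at Week 20". Section 1.4 and Table 2 label that visit FU, and 4.3 is the follow-up period ending at Week 20. The first sentence of 8.5.3.2 separates on-treatment from the follow-up period. Where the section means every visit, it says so for laboratory data, urinalysis and vital signs. Physical examination is the exception, so Week 20 is the natural reading.

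**Step 2: which examinations can supply a shift.** Brief examinations record only whether they were done, so they give no normal/abnormal result. That leaves these complete examinations after Week 0:

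| Patient | Complete examinations after Week 0 | Used on the natural reading |
|---|---|---|
| Completer | Week 12, Week 20 (2) | Week 20 (1 of 2) |
| Early discontinuer without Week 20 | IPD (1) | none (0 of 1) |

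Over the whole schedule, one of three post-baseline complete-examination columns (Week 12, IPD, Week 20) is used.

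**Step 3: the rule applied to records, with Week 0 as baseline.**

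- Normal at Week 0, abnormal at Week 12, normal at Week 20: no shift.
- Normal at Week 0, normal at Week 12, abnormal at Week 20: shift.
- Normal at Week 0, IP stopped, abnormal at IPD, no Week 20 examination: no entry.

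**Step 4: whether the adverse-event route catches what the table drops.** Sections 5.2.1 and 7.1.3.6 require a new or aggravated finding that is clinically significant or relevant to be reported as an AE. AEs are collected through Week 20 (7.1.3.1), and 8.5.3.2 counts them by study period and lists them by patient. Two kinds of finding can fall outside both displays:

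- findings the investigator judges not significant or relevant;
- asthma signs such as wheeze, which 7.1.3.7 records as AEs only if serious, if they lead to study discontinuation, or if new to the patient or out of keeping with the asthma history.

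**Step 5: the baseline.** Complete examinations are scheduled at both Visit 1 (Table 1) and Week 0 (Table 2). A patient normal at Visit 1, abnormal before the first dose at Week 0 and abnormal at Week 20 has a shift if Visit 1 is baseline and none if Week 0 is. Section 8.4.2 points to Week 0 and 5.2.1 to Visit 1. The AE rule in 7.1.3.6 refers to the baseline assessment without saying which.

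**The case against.** Several points on the other side have force.

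- **The sentence does not say only, and does not name Week 20.** The protocol sometimes uses follow-up more loosely: 8.5.3.1 speaks of total follow-up time. This makes the wording ambiguous but does not make it adequate. A sentence that can be read two ways, beside three that cannot, needs correcting.
- **Section 8.4.2 may already cover it.** It lists physical examination among the safety data and then calls for change to each scheduled time point. But it limits this to relevant measurements, which does not clearly reach a normal/abnormal judgement, and 8.5.3.2 is the more specific text.
- **The contrast with laboratory data has a rationale.** Under 7.1.3.6, deterioration in mandated laboratory values and vital signs becomes an AE only if it meets SAE criteria or causes discontinuation of IP, so those data depend more on visit-by-visit tables. Examination findings have a wider AE route. This stands and lowers the weight of the point, but the route has the gaps in step 4.
- **Shift-table columns are commonly left to the SAP.** That is so, but here the protocol states a rule and does not defer it.

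A reader might also infer more than the documents support:

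- **That the trial would miss these abnormalities.** It would not: clinically relevant ones must be reported as AEs.
- **That all early discontinuers are lost.** Section 4.3 describes Week 20 for completers, but nothing says discontinuers skip it. The loss applies to those without a Week 20 examination.
- **That falling drug levels measure the loss.** The protocol equates 16 weeks with 5 half-lives, so one half-life is 16/5 = 3.2 weeks. Simple first-order decay leaves 2^(-4/3.2) ≈ 42% of the last-dose level at Week 12 and 2^(-12/3.2) ≈ 7% at Week 20. This shows that the two examinations differ in exposure, not how many abnormalities would appear and resolve between them.
- **That pre-dose findings will be counted as shifts.** Section 8.4.2 gives Week 0 as the baseline for change. The 5.2.1 wording needs reconciling but does not establish that Visit 1 will be used.

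**Conclusion.** The point holds as a low-weight reporting defect. On the natural reading of 8.5.3.2, the shift table uses one of a completer's two complete post-baseline examinations and none for an early discontinuer without a Week 20 examination. Abnormalities at Week 12 or IPD that resolve by Week 20 are absent from the table. Those judged not clinically relevant, and asthma signs limited by 7.1.3.7, may appear neither there nor among the AEs.

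This rests on follow-up meaning the Week 20 visit or period, and on 8.4.2 not overriding the more specific sentence. The documents do not allow an estimate of how many findings would be affected. The display is descriptive, and no primary endpoint depends on it.

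**What to change.** Replace the physical-examination sentence in 8.5.3.2 with wording such as: *Normal-to-abnormal shifts from the pre-dose Week 0 complete examination to every later complete examination (Week 12/EOT, IPD, Week 20) will be tabulated by treatment group.*

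Reconcile the Visit 1 baseline statement in 5.2.1 with the Week 0 baseline in 8.4.2, so that the shift table has one stated baseline and it is clear which assessment 7.1.3.6 refers to.

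The cost is one or two sentences and a few table columns. No visit, procedure or data item is added.
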